## Endpoints and Relevant Variables

Refer to separate file for list of relevant variables for each endpoint, along with relevant datasets and endpoint description (“TRAIL1 endpoints and dataset variable names.xlsx” and “Primary & Secondary Outcomes” tab.)

## **Primary and Secondary Endpoints and Relevant Variables**

*Composite endpoint of decline from baseline in percent predicted FVC of 10% or greater or death during study period.*

- FVC (percent predicted) at baseline
  - Last FVC (percent predicted) while on study
- Decline from baseline in percent predicted FVC is (last percent predicted FVC while on study) - (percent predicted FVC at baseline)
- Death (yes/no) while on study

*Decline from baseline in percent predicted FVC of 10% or greater during study period.*

- FVC (% predicted) at baseline
  - Last FVC (% predicted) while on study
- Decline from baseline in percent predicted FVC is (last percent predicted FVC while on study) - (percent predicted FVC at baseline)

*Frequency of progressive disease as defined by OMERACT: Relative decline from baseline in percent predicted FVC of  $\geq 10\%$ , or relative decline from baseline in percent predicted FVC  $\geq 5\%$  and  $< 10\%$ , and  $\geq 15\%$  relative decline from baseline in percent predicted DLCO (Khanna, Mittoo et al. 2015)*

- FVC (percent predicted) at baseline
  - Last FVC (percent predicted) while on study
- Relative decline from baseline in percent predicted FVC = [(Last FVC(percent predicted) – Baseline FVC (percent predicted))/Baseline FVC (percent predicted)]\*100
- DLCO (percent predicted) at baseline
  - Last DLCO (percent predicted) while on study

Relative decline in percent predicted DLCO = [(Last DLCO (percent predicted) – Baseline DLCO (percent predicted))/Baseline DLCO (percent predicted)]\*100

If DLCO (percent predicted) is missing, TLCO (percent predicted) will be substituted.

*Change from baseline over study period in FVC (L)*

- FVC (L) at baseline
- Last FVC (L) while on study

*Change from baseline over study period of percent predicted FVC*

- FVC (percent predicted) at baseline
- Last FVC (percent predicted) while on study

*Slope of percent predicted FVC over study period*

- All available percent predicted FVC measurements and dates while on study

*Slope of absolute FVC over study period*

- All available FVC measurements and dates while on study

*Time to decline of 10% or greater in percent predicted FVC at death over study period*

- Baseline percent predicted FVC and randomization date
- All measurements of percent predicted FVC while on study and date
- Death date, death indicator
- Last study visit date

*Proportion of participants with all-cause mortality*

- Death date present or absent

*Proportion of participants with all-cause hospitalization*

- Hospital admission date present or absent

*Proportion of participants with hospitalization for respiratory cause*

- Hospital admission date
- Hospitalization reason

*Number of participants with acute exacerbations requiring hospitalizations*

- Hospital admission date(s)
- Hospitalization reason for each admission

*Proportion of participants with and number of participants with treatment-emergent/treatment-related AEs*

- Participants with at least one treatment emergent AE (yes/no for each participant) where treatment emergent is defined as the AE onset date being greater than or equal to the date of the first dose of study medication, or the randomization date if the date of the first dose of study medication is missing
- Number of treatment-related AEs for each participant while on study

*Proportion of participants with and number of treatment-emergent/treatment-related SAE (a subset of AEs)*

- Participants with at least one treatment emergent SAE (yes or no for each participant)
- Number of treatment-related SAEs for each participant while on study

*Proportion of participants with and number of AEs leading to early discontinuation of study treatment*

- Early treatment discontinuation (yes or no for each participant)

- Reason for each early treatment discontinuation
- Number of AEs per participant where the action is “permanent discontinuation or withdrawn from study medication

*Proportion of participants with and number of participants with treatment-emergent death, transplant, and transplant then death*

- Cause of death
- Cause of transplant

*Proportion of participants with and number of participants with treatment-emergent RA-ILD-related mortality*

- Cause of death

*Change from Baseline to Week 52 in dyspnea, as measured by the Dyspnea 12 questionnaire*

- Baseline Total Dyspnea 12 questionnaire score and date
- Last Total Dyspnea 12 questionnaire score on study and date

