### **Endpoints**

#### **Primary Endpoint**

The primary outcome variable of this study is the incidence of the composite endpoint of decline from baseline in percent predicted FVC of 10% or greater or death during the study period. The primary endpoint will be analyzed using the ITT population

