#### **Secondary Endpoints**

Secondary outcome for this study will be assessed from baseline to the end of study for each patient. The following secondary outcomes will be analyzed using the ITT population:

1. Incidence of a decline from baseline in percent predicted FVC of 10% or greater during the study period.
2. Frequency of progressive disease as defined by Outcome Measures in Rheumatology (OMERACT): Relative decline from baseline in percent predicted FVC of  $\geq 10\%$ , or relative change from baseline in percent predicted FVC  $\geq 5\%$  and  $< 10\%$ , and  $\geq 15\%$  relative decline in diffusing capacity of lung for carbon monoxide (DLCO) (Khanna, Mittoo et al. 2015)
3. Change from baseline to end of study in absolute value of FVC
4. Change from baseline to end of study of percent predicted FVC
5. Slope of percent predicted FVC over 52-week treatment period
6. Slope of absolute value of FVC over study period
7. Time to decline of 10% or greater in percent predicted FVC or death while on study
8. Change from Baseline to end of study in dyspnea, as measured by the Dyspnea 12 questionnaire

The following secondary outcomes will be analyzed using the as-treated population:

9. Proportion of participants with all-cause mortality
10. Proportion of participants with all-cause hospitalization
11. Proportion of participants with hospitalization for respiratory cause
12. Number of acute exacerbations requiring hospitalizations
13. Proportion of participants with and number of treatment-emergent adverse events (AEs)
14. Proportion of participants with and number of treatment-emergent serious adverse events (SAEs)
15. Proportion of participants with and number of treatment-emergent/treatment-related AEs
16. Proportion of participants with and number of treatment-emergent/treatment-related SAEs
17. Proportion of participants with and number of AEs leading to early discontinuation of

study treatment

18. Proportion of participants with and number of treatment-emergent death or transplant

19. Proportion of participants with and number of treatment-emergent RA-ILD-related mortality

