## **Efficacy Analyses**

All efficacy variables will be listed by participant within study center. Data will be summarized by treatment arm using descriptive statistics (N, Mean, Standard Deviation, Minimum, and Maximum) for continuous efficacy variables. Number and percent will be presented for categorical efficacy variables. Columns will be Placebo and Pirfenidone. The primary efficacy population will be the ITT population, where all randomized participants are included according to their randomized treatment arm.

The primary efficacy analysis for this trial has a binary composite outcome. (A) Patients will be

categorized based on their decline since baseline in percent predicted FVC of 10% or greater during study period. (B) Patients will also be categorized based on death during study period. The composite primary endpoint is the occurrence of either (A) or (B) during the study period. Comparisons between treatment arms will be performed using a mixed effect logistic regression model, adjusting for the continuous fixed covariate baseline percent predicted FVC and the fixed binary covariate HRCT pattern. Treatment arm will be an independent fixed effect and study center will be a random effect in the analysis (Kahn, 2014). The likelihood-ratio test will be used to test for differences between treatment arms. Treatment arm will be tested at a 2-sided 5% significance level. The components of the primary endpoint will be similarly analyzed.

The adjusted odd ratios together with 95% confidence interval and p-value will be used to quantify the effect of treatment, comparing pirfenidone with placebo as the reference. The data will be coded such that an odds ratio less than 1.0 will indicate that pirfenidone is protective. Assumptions for models will be assessed by examining the plots for the residual values. If data sparseness causes model fitting problems, the model will be simplified by using study network instead of study center as a random effect and/or eliminating the random center (or network) effect.

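### The SAP writes FVC and DLCO decline as last minus baseline, the wrong sign for its positive thresholds, and states the last-value rule for the primary event only there

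*SAP*

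**What the plan says.** **Formulas.** The SAP section Primary and Secondary Endpoints and Relevant Variables lists, under "Composite endpoint of decline from baseline in percent predicted FVC of 10% or greater or death during study period", the baseline value, the last on-study value and death, and then gives the rule "Decline from baseline in percent predicted FVC is (last percent predicted FVC while on study) - (percent predicted FVC at baseline". The same line is repeated for secondary endpoint 1, the FVC criterion without death. For the OMERACT endpoint it begins "Relative decline from baseline in percent predicted FVC = [(Last FVC(percent predicted" and "Relative decline in percent predicted DLCO = [(Last DLCO (percent predicted". Each then subtracts the baseline value, divides by baseline and multiplies by 100.

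**Thresholds.** All are positive: 10 or more for the absolute decline; for OMERACT, a relative FVC decline of at least 10%, or of 5% to under 10% together with a relative DLCO decline of at least 15%. The section has no minus sign, absolute value or negative cut-off.

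**Direction.** Efficacy Analyses states: "The data will be coded such that an odds ratio less than 1.0 will indicate that pirfenidone is protective".

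**Timing.** The derivation list assigns the last on-study FVC to the binary endpoints. It asks for all dated measurements only for the two slopes and for time to decline. The SAP's Primary Endpoint section reads "decline from baseline in percent predicted FVC of 10% or greater or death during the study period", and Efficacy Analyses reads "The composite primary endpoint is the occurrence of either (A) or (B) during the study period". The SAP sections Planned Sample Size and Missing Data, and protocol 10.2.1 and 10.4.2, describe an event attained by Week 52. Protocol 4.2.1 refers to the treatment period. None of these applies a last-value rule to the binary event or points to the derivation list.

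**Other source.** The SAP section Endpoints and Relevant Variables refers to a separate spreadsheet with endpoint descriptions. It was not available for this review.

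**The concern.** The primary composite is the trial's single pre-specified primary endpoint, tested at a two-sided 5% level, and the derivation list holds the only formula for its FVC part. A programmer who codes that formula against its threshold scores improvement as an event and deterioration as none.

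One who notices the problem has to repair it unaided, and could do so in two ways. Reversing the sign is right. Taking the absolute value would still count gains as events.

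The protocol's background does not set a convention: section 2.1.3.3 reports FVC decline as negative numbers, while the account of the later 52-week IPF trial reports it as positive millilitres. For the OMERACT middle band, item 2 of the SAP's Secondary Endpoints says change rather than decline, so in that item the wording alone does not fix the direction.

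The timing question is smaller. Secondary endpoint 7, "Time to decline of 10% or greater in percent predicted FVC or death while on study", covers the same composite but is derived from every FVC measurement. A participant who falls by 10 points at Week 26 and recovers by Week 52 is an event there, but not in the primary endpoint under the last-value rule.

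**Working it through.** **Plan's own figure.** Inputs from protocol 10.2.1: proportions 0.32 and 0.16, two-sided 5%, 85% power. With mean proportion 0.24 and pooled variance:

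n = [1.960 × √(2 × 0.24 × 0.76) + 1.036 × √(0.32 × 0.68 + 0.16 × 0.84)]² / 0.16² = (1.184 + 0.615)² / 0.0256 ≈ 126.4, rounded up to 127 per arm.

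This matches the protocol. The sample size is not in dispute, and correcting the sign does not alter it.

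**Sign check.** The participants below are hypothetical. *As written* is last minus baseline; *corrected* is baseline minus last. The relative versions divide by baseline and multiply by 100.

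| Measure | Baseline → last | As written | Threshold met? | Corrected | Threshold met? |
|---|---|---|---|---|---|
| % predicted FVC, absolute, ≥10 | 70 → 58 | 58 − 70 = −12 | no | +12 | yes |
| % predicted FVC, absolute, ≥10 | 70 → 81 | 81 − 70 = +11 | yes | −11 | no |
| FVC, relative, ≥10% | 70 → 62 | −8/70 = −11.4% | no | +11.4% | yes |
| FVC, relative, 5% to <10% | 70 → 65 | −5/70 = −7.1% | no | +7.1% | yes |
| DLCO, relative, ≥15% | 50 → 42 | −8/50 = −16.0% | no | +16.0% | yes |

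Every fall large enough to meet its criterion is missed as written, and the gain is counted. The last two rows together should make a participant progressive under the OMERACT middle band; as written, neither part is met. The death component has no formula and is unaffected.

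**Where the expression fits.** Protocol 10.4.2 gives last minus baseline for the continuous change outcomes, and it is right for those. The derivation list uses the same subtraction but labels it decline.

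**Timing, passages side by side.**

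- The derivation list repeats the primary endpoint's title and assigns the last value to it. For time to decline it assigns all measurements. That contrast looks deliberate.
- The defining sections speak of occurrence over a period, or of an endpoint attained by Week 52. Both phrasings also fit a crossing at any of the Week 13, 26, 39 or 52 spirometry visits.
- The more specific text probably governs, but nothing in the general text says so.

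**The case against.** The best reply is that nobody would run this backwards. The word decline stands in the endpoint titles, the odds-ratio coding treats an event as harmful, and a literal reading would make a rise in FVC progressive disease. For the two absolute criteria, the derivation list gives a signed difference and never writes the inequality beside it. All of this stands, and it limits the point to a drafting error. It does not make the formulas right: a quantity named decline, compared with a positive threshold, has to be positive when function falls.

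On timing, the reply is that the derivation list already answers the question. The planning rates support it: protocol 10.2.1 takes them from the IPF trial that the background reports as 16.5% against 31.8% at Week 52, which fits a final-value reading. A binary final-value endpoint and a time-to-first-crossing endpoint also naturally give different counts. This largely stands, and it is why timing is raised only for confirmation.

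The spreadsheet may settle both matters. If it has the right sign, the SAP text contradicts it and still needs correcting.

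**Conclusion.** The sign is wrong as written in four formulas under three endpoints: the primary composite, secondary endpoint 1 and the OMERACT endpoint. Two of the four are the same line. Confidence is high, because the finding rests only on the text and on subtraction.

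A reader might infer that the analysis would be reversed, that the odds ratio would point the wrong way, or that most primary events would be lost. At the planning rates, 123 randomised participants would give about 0.32 × 61.5 + 0.16 × 61.5 = 19.7 + 9.8 = 29.5 composite events, and a literal derivation would leave unscored those that are FVC falls without death. The documents do not support expecting this. Their titles and coding show the intended direction, and they do not split the rates between falls and deaths.

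A reader might also infer that the primary endpoint's timing is contradictory. It is not: one passage is specific and the others are general. Confidence that the last-value rule is intended is moderate. How many participants the two timing readings would classify differently cannot be derived, because the documents give no standard deviation for FVC change or for visit-to-visit variation.

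Overall the point is minor to should-fix.

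**What to change.** 1. In the derivation list, define absolute decline as baseline minus last on-study percent predicted FVC, in both places. Define relative FVC and DLCO decline as baseline minus last, divided by baseline, times 100. Leave the thresholds as they are.
2. Check that the endpoint spreadsheet and the analysis code use the same direction, without an absolute value.
3. Have the sponsor confirm that the binary FVC event is scored from the last on-study value, and state what closes the on-study period (Week 52 with its visit window, or a later contact). If confirmed, refer to the derivation list from Primary Endpoint and Efficacy Analyses. Note that the attained-by-Week-52 wording in Planned Sample Size, Missing Data and protocol 4.2.1, 10.2.1 and 10.4.2 is to be read that way.
4. Add one sentence saying that secondary endpoint 7 uses all measurements, so its event count may differ from the primary.

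The cost is wording alone. The SAP says that it is finalised before the database closes, so the change belongs before lock. It needs no new data, no change of model and no new sample-size calculation. Reversing the sign leaves the intended derivation as it is.

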#### Exchange of Single Case Reports

Serious Adverse Events (SAEs), pregnancy reports, where the participant has been exposed to the Product, will be sent on a MedWatch or CIOMS I form to the Roche contact via the DCC. Transmission of these reports (initial and follow-up) will be either electronically or by fax and within the timelines specified below:

- SADRs  
Serious AE reports that are related to the Product or where the causality is assessed as unknown or not provided shall be transmitted to Roche via the Data Coordinating Center (DCC) within fifteen (15) calendar days of the awareness date.
- Other SAEs  
Serious AE reports that are unrelated to the Product shall be transmitted to Roche via the DCC within thirty (30) calendar days of the awareness date.
- Pregnancy reports  
While such reports are not serious AEs or Adverse Drug Reactions (ADRs) per se, any reports of pregnancy, where the fetus may have been exposed to the Product, shall be transmitted to Roche via the DCC within thirty (30) calendar days of the awareness date. Pregnancies will be followed-up until the outcome of the pregnancy is known, whenever possible, based upon due diligence taken to obtain the follow-up information.

[Note: For all reports, an acceptable format includes MedWatch or CIOMS I form, or Roche approved reporting forms. If the Sponsor is unable to use these formats then line-listings can be used as detailed in the Global: Investigator Initiated Study Safety Data Exchange Management (WI-0100195).]

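### Read literally, the SAP derives the proportion with treatment-related AEs and SAEs from any treatment-emergent event, so the proportion does not match its own count

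*SAP*

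**What the plan says.** The Secondary Endpoints list in the SAP has four adverse-event items, each asking for a proportion of participants and a number of events:

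- item 13: "Proportion of participants with and number of treatment-emergent adverse events (AEs"
- item 14: "Proportion of participants with and number of treatment-emergent serious adverse events (SAEs"
- item 15: "Proportion of participants with and number of treatment-emergent/treatment-related AEs"
- item 16: "Proportion of participants with and number of treatment-emergent/treatment-related SAEs"

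Protocol section 4.2.2 lists the same four as items 12 to 15.

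The section Primary and Secondary Endpoints and Relevant Variables has entries for only two of them, both headed as treatment-emergent/treatment-related. Under the AE heading the participant-level variable is "Participants with at least one treatment emergent AE (yes/no for each participant". It comes with a definition of treatment-emergent based on onset date, and no mention of relatedness. Under the SAE heading, "Proportion of participants with and number of treatment-emergent/treatment-related SAE (a subset of AEs", the variable is "Participants with at least one treatment emergent SAE (yes or no for each participant", again without relatedness. In both entries the second bullet is a per-participant count that is limited to treatment-related events during the time on study.

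Protocol section 8.3 has the investigator grade each AE as Not, Possibly or Probably Related.

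**The concern.** The relatedness condition is attached to the number and not to the proportion. An analyst who programs the entry as written would label as treatment-related a proportion that contains every participant with any treatment-emergent event, whatever its grade. The proportion and the count on the same line would then describe different sets of events.

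Protocol section 2.2 states safety and tolerability as a purpose of the trial, and events attributed to the drug are part of that picture. Related events are a subset of all events, so a mislabelled proportion can only equal or exceed the true one in each arm. If most participants have some adverse event, it could also hide a difference between arms in related events.

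**Working it through.** No figure in the plan can be reproduced here. The check is a comparison of texts, followed by a short piece of algebra on the consequence.

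**1. What is asked for and what is derived**

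| Endpoint (SAP list) | Proportion needs | Number needs | Flag given | Count given |
|---|---|---|---|---|
| 13, AEs | any treatment-emergent AE | all treatment-emergent AEs | no entry | no entry |
| 14, SAEs | any treatment-emergent SAE | all treatment-emergent SAEs | no entry | no entry |
| 15, related AEs | a treatment-emergent and related AE | the same events | any treatment-emergent AE | related AEs on study |
| 16, related SAEs | a treatment-emergent and related SAE | the same events | any treatment-emergent SAE | related SAEs on study |

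**2. Two ways to read the entries**

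- *Literal.* Both bullets serve the endpoint named in the heading. The flag for 15 is then the variable that 13 calls for, and the flag for 16 is the one that 14 calls for. The proportions are identical by construction. The counts are not, because they carry the relatedness condition.
- *Merged.* The slash in the heading joins 13 with 15 and 14 with 16; the first bullet serves the all-event endpoint and the second the related one. Nothing is duplicated, but the related proportion (15, 16) and the all-event number (13, 14) have no derivation.

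On neither reading does this section define the proportion with a related event.

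**3. Whether other sections supply it**

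- SAP, Safety Analyses, counts each participant once for AE incidence and for any sub-classification of it. SAP, Adverse Events, plans summaries by relationship to study drug. Together these give participant-level AE tabulations by relatedness. They do not say which of the three protocol grades make an event related for endpoints 15 and 16, and they do not override the flag.
- SAP, Deaths, Serious AEs and other Significant AEs, does not repeat the split by relationship for SAEs.

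**4. Related gaps in the same entries**

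- The counts are bounded by time on study and are not restricted to treatment-emergent events.
- Treatment-emergent has two definitions. The entry for endpoint 15 uses an onset date on or after the date of first dose (the randomization date if that is missing). The Adverse Events section uses first occurrence or worsening after the first dose. A pre-existing event that worsens on treatment meets the second and, if its original onset date is kept, not the first.

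**5. Direction and size of the effect on the literal reading**

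In each arm let *A* be the proportion with any treatment-emergent event and *R* the proportion with a related one. The overstatement is *u = A − R*, the share of participants whose treatment-emergent events are all unrelated; it is at least 0. The reported between-arm difference is the true related difference plus (*u* pirfenidone − *u* placebo).

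The documents give no rates for *A* or *R*, so the following are assumptions that only show the mechanism. With *A* = 90% in both arms and *R* = 65% against 40%, *u* is 90 − 65 = 25 and 90 − 40 = 50 points. The true difference is 65 − 40 = 25 points and the reported one is 25 + (25 − 50) = 0. With *R* = 65% in both arms, *u* is 25 in each, and the true and reported differences are both 0. So between these two assumed cases the loss runs from 0 to 25 points. The documents do not indicate where in that range, or outside it, the trial would fall.

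**The case against.** The strongest reply is that this section mainly lists input variables. RA-ILD-related mortality has only cause of death beneath it, and respiratory hospitalization has only an admission date and a reason; nobody would conclude that every death or admission counts. Likewise, a related proportion can be obtained as the share of participants with a related count of at least one. The SAP also refers to a separate spreadsheet for variables and endpoint descriptions, which is not among the documents reviewed and may contain the condition.

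Part of this stands. The intended proportion is recoverable, and the planned AE summaries by relationship mean that related AEs would still be tabulated. But the bullets in question are written as yes/no participant variables, one with its own definition of treatment-emergent, and the SAP does not say to use a count of at least one. If the spreadsheet does require relatedness, it disagrees with the SAP text read literally, and the two need aligning.

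A reader might go further in three ways that the documents do not support:

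- *That endpoints 15 and 16 as a whole repeat 13 and 14.* Only the proportion half does, and only on the literal reading; the counts require relatedness.
- *That related AEs would go unreported, or that a difference between arms would be lost.* The Adverse Events section plans the split by relationship, and the size of any distortion rests on assumed rates.
- *That a missing grade must be counted as related.* Protocol section 8.2.2 groups "Serious AE reports that are related to the Product or where the causality is assessed as unknown or not provided", but that passage sets deadlines for sending SAE reports to the supporting company. It is not an analysis rule and does not cover non-serious AEs.

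**Conclusion.** The point holds for the proportion half of two of the 19 secondary endpoints. On the literal reading that half duplicates endpoints 13 and 14 and is inconsistent with its own count; on the merged reading it has no derivation, and neither does the all-event number. The gap is more exposed for SAEs, where no split by relationship is planned outside this section.

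Severity is minor to moderate. The primary endpoint is untouched, protocol sections 10.2.2 and 10.4.2 treat secondary outcomes as exploratory, and the SAP's Multiple Testing section calls them hypothesis-generating. The conclusion assumes that the SAP text governs and that the unseen spreadsheet does not already settle the matter. The direction of the error in each arm (equal or too high) follows from the definitions. Its size, and its effect on the contrast between arms, cannot be determined from the documents.

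**What to change.** In Primary and Secondary Endpoints and Relevant Variables:

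1. Give endpoints 13 to 16 separate entries, each with a proportion and a number.
2. For 13 and 14, use all treatment-emergent AEs or SAEs, with no relatedness condition.
3. For 15 and 16, define the proportion as participants with at least one AE or SAE that is both treatment-emergent and graded Possibly or Probably Related on the protocol section 8.3 scale. Count the same set of events for the number.
4. State how a missing relatedness grade is handled. Counting it as related is one conservative option; the protocol does not require it.
5. Adopt one definition of treatment-emergent here and in the Adverse Events section, and bring the separate spreadsheet into line.

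These choices should be fixed before unblinding, which is consistent with protocol section 10 and with the SAP's own commitment to be final before the database closes. The cost is a few lines of SAP text and a simple filter in the program. The relatedness grade is already collected and already appears in the planned AE listings.
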